8.1.2. Assumption Testing

No assumption testing will be performed.

8.1.3. Missing Data Handling

No imputation will be made for the missing values for the primary approach.

8.1.4. Subgroup Analysis

The primary endpoint will be summarized using the following subgroups:

- Age categories (≥ 18 to < 40 , ≥ 40 to < 65 , ≥ 65),
- Gender (Male, Female)
- Baseline Body weight at screening (kg) with grouping (< 70 , ≥ 70 to < 100 , ≥ 100),
- Region (US [non-PSG and PSG], Europe and ROW).
- Baseline IGA (moderate [IGA=3] and severe [IGA=4])
- Baseline moderate to severe EASI (≤ 21 , > 21)
- Baseline severe EASI (< 25 , ≥ 25)
- Baseline SCORAD (≤ 50 , > 50)
- Baseline peak pruritus NRS (< 7 , ≥ 7)
- Previous use of systemic immunosuppressants for AD (Yes, No)

List of coded terms for systemic immunosuppressants (medications) used for AD will be provided by SANOFI.

Results will also be illustrated with forest plots.

8.1.5. Sensitivity Analysis

If a specific weekly average for the sleep quality NRS was derived using 3 or less assessments, such assessments will be set to missing in any sensitivity analysis.

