6.5.3 Rescue medicine

If medically necessary (ie, to control intolerable AD symptoms), rescue treatment for AD may be provided to study patients at the discretion of the investigator. If possible, Investigators should attempt to limit the first step of rescue therapy to high-potency TCS and/or TCIs, and escalate to systemic medications only for patients who do not respond adequately after at least 7 days of topical treatment. Investigators should make every attempt to conduct efficacy and safety assessments (eg, disease severity scores, safety labs) immediately before administering any rescue treatment. An unscheduled visit may be used for this, if necessary.

Note that:

1. Those who receive high-potency or superpotent TCS will be allowed to continue study treatment.
2. Those who receive systemic corticosteroids or non-steroidal systemic immunosuppressive drugs (eg, CSA, AZA, MTX, MMF, or JAK inhibitors) will discontinue study treatment for the duration of rescue + 5 half-lives of the rescue agent.

3. All patients will be encouraged to complete the entire schedule of study visits and assessments whether or not they complete study treatment and whether or not they receive rescue treatment for AD.

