9.2 SAMPLE SIZE DETERMINATION

The sample size calculations were based on the subset of patients who reported ≥ 5 units of baseline sleep loss and ≥ 3 units of baseline pruritus scores on the SCORAD instrument in a previous study (AD1424) evaluating efficacy of dupilumab for AD.

Since no previous data are available on daily sleep on the NRS scale, the SCORAD sleep component (VAS) data was used as a basis for the sample size determination for the primary endpoint. The variability (standard deviation) estimate for the subset of patients mentioned above was 37% for the % change from baseline to week 12. Given the uncertainty in the variability from this variable to the NRS weekly average sleep score, the above variability was inflated by ~20%, and assumed to be 44% for the primary sleep parameter. With these assumptions, a total sample of 150 (50 in placebo and 100 in dupilumab group) patients will provide 90% power (alpha = 0.05, 2-sided) to detect a treatment difference of 25% (effect size, $\Delta/\sigma = 0.57$) for the percent change from baseline.

For secondary actigraphy endpoints, sample size estimates are provided in reference to nemolizumab Ph2 data at week 4. For TST, to detect a 30 minutes difference between treatments: (2:1 allocation ratio; alpha=0.05, 2-sided), assuming the same variability at week 16 weeks as seen for nemolizumab at week 4 (=56 min), then 167 subjects are needed to provide 90% power. Furthermore, the proposed sample size would have >90% power to detect a difference of 10% for change from baseline in actigraph based sleep efficiency, assuming a variability of 11% (alpha=0.05, 2-sided). The variability estimate was based on (8) for actigraphy based sleep efficiency at week 4, inflated by 50% to account for possible increase in variability over time (from week 4 to week 16). Of note, the data used for actigraphy parameters are limited.

Allowing for drop outs, a total of approximately 201 patients will be enrolled in the study.

Considering the uncertainty of the variability of the primary endpoint, when data are available for this endpoint from about 50% of the patients, the variability will be assessed in a blinded manner, and the sample size will be re-estimated. If the re-estimated sample size is higher than the original estimate, the sample size may be increased accordingly, not to exceed a total of 150 additional patients.

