Primary endpoint	Percentage change from baseline to Week 12 in sleep quality NRS	ITT	
 Discontinuation or interruption of study treatment due to Covid-19 pandemic, off-treatment data will be set as missing (hypothetical strategy). The assessments after patients resume treatment will be used. Discontinuation or interruption of study treatment not due to Covid-19 pandemic, all data collected following schedule after the treatment discontinuation will be used in the analysis (treatment policy strategy). Taking rescue medications ^b prior to Week 12: data will be set to missing values after the medication usage (hypothetical strategy) Taking prohibited medications ^b that affect sleep: All sleep related assessments (sleep NRS, SCORing subjective sleep loss scores, PROMIS sleep disturbance short form 8a individual question scores, ESS, actigraphy data) on that corresponding night will be set to missing (hypothetical strategy) Taking prohibited medications ^b that affect AD, data will be set to missing values after the medication usage (hypothetical strategy) 	A mixed effect model for repeated measures (MMRM) under the missing at random (MAR) framework will be used. The MMRM will include treatment, baseline value, randomization stratum, visits (up to week 12), treatment by visit interaction, and baseline sleep quality NRS by visit interaction terms all as fixed effects. Randomization stratum, treatment and visits will be considered as categorical parameters. No explicit imputation will be done for missing data.
Secondary objective: To evaluate the effect of dupilumab on objective and subjective quantitative sleep parameters, AD related outcomes, and daytime consequences of sleep deprivation.				

Endpoint Category (estimand)	Estimands			Population-level summary (Analysis and missing data handling)
	Endpoint(s) ^a	Population	Intercurrent event(s) handling strategy	
Secondary endpoint (treatment policy strategy/hypothetical strategy)	Change or percent change from baseline in Sleep and AD related outcomes	ITT	Same as the primary endpoint	The same MMRM with the baseline values corresponding to the outcome variables.

^a Additional key secondary endpoints are not included in this table but would be handled with a similar strategy as the endpoint type (ie continuous, binary, time-to-event) at other weeks. The key secondary endpoints are listed in [Section 8.2.23](#).

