3.1. Overall Study Design and Plan

This is a Phase IV, prospective, 2:1 randomized, multinational, multicenter study, with a 12-week double-blind placebo-controlled period, followed by a 12-week open label extension to evaluate the effect of dupilumab on sleep in adult patients with moderate to severe AD.

[figure not shown]
Approximately 201 participants will be randomly assigned to study intervention in a 2:1 dupilumab to placebo ratio from multiple sites globally such that at least 150 evaluable participants (100 in the active group and 50 in placebo) complete the double-blind portion (to week 12) of the study.

The study will comprise of:

- Screening Period 1 (Day -28 to -8): Patients will be evaluated according to inclusion and exclusion criteria
- Screening Period 2 (Day -7 to -1; pre-baseline assessments): eligible patients will complete the daily sleep quality, daily pruritus, skin pain, skin sensitivity, and touch skin burn, sleep diary, and will wear an actigraph at night-time during the 7 days immediately preceding the Baseline visit (Day 1). If preferred by the patient and the investigator for logistical reasons, screening can be done during a single on-site visit. In that case, all procedures planned at screening 1 and screening 2 should be done during this single screening visit. Importantly, this single screening visit will have to be done at least 7 days before the baseline visit, as patients should wear the actigraph and complete the diary for 7 days before baseline.
- Baseline (Day 1): Patients who remain eligible will be randomized
- 12-week double-blind placebo-controlled period: Patients will be randomized to receive dupilumab or placebo
- 12-week open-label extension period: following completion of double-blind period, patients randomized to dupilumab will continue to receive active treatment for open-label period, whereas patients randomized to placebo will receive active treatment with dupilumab.

The maximum study duration per participant will be 28 weeks. A patient is considered to have complete the study if he/she has completed all phases of the study including the last scheduled visit shown in the Schedules of Activities (see [Appendix 15.2](#)).

Figure 3-1 Study Plan

Abbreviations: q2w=every 2 weeks

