8.1.6. Supplementary Analyses

Not applicable.

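### No planned analysis of the primary endpoint departs from missing at random, so the report cannot show how far the estimate depends on the course assumed for patients who stop treatment and leave

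*SAP*

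**What the plan says.** - **Primary model.** SAP 8.1.1 and Table 3.1.2 specify an MMRM under MAR. SAP 8.1.3 adds that missing values are not imputed.
- **Sensitivity analysis.** SAP 8.1.5 plans one: "If a specific weekly average for the sleep quality NRS was derived using 3 or less assessments, such assessments will be set to missing". The summary table in SAP 15.1 confirms that the same MMRM is then refitted without imputation.
- **Supplementary analyses.** The section "8.1.6. Supplementary Analyses" is marked not applicable.
- **Discontinuation not due to Covid-19.** In Table 3.1.2, "all data collected following schedule after the treatment discontinuation will be used in the analysis (treatment policy strategy"). The last column of that row names MMRM under MAR for whatever is still missing.
- **Covid-19 discontinuation and rescue.** Both have a hypothetical strategy in Table 3.1.2. Off-treatment data (Covid-19) and data after rescue are set to missing.
- **Follow-up.** Protocol 6.5.3 states: "All patients will be encouraged to complete the entire schedule of study visits and assessments whether or not they complete study treatment". The same sentence extends this to patients who receive rescue. Protocol 7.1.1 also keeps patients in the study after they stop treatment.

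**The concern.** A sensitivity analysis of a MAR model should change the MAR assumption. This one removes some observed weeks and keeps the assumption, so agreement between the two fits says nothing about it.

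The assumption carries most weight for patients who stop treatment for a reason other than Covid-19 and then leave. A treatment-policy aim asks for their Week 12 outcome whatever treatment they are then on. The MMRM fills that gap implicitly from patients in the same arm with a similar history, most of whom are still on treatment. SAP 8.1.7 argues that MAR is reasonable for data missing because of Covid-19. It gives no such argument for other discontinuation or for rescue.

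At stake is the size of the sleep benefit that the trial will report.

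**Working it through.** **Inputs from the documents**
- Difference, alpha and power (Protocol 9.2): "patients will provide 90% power (alpha = 0.05, 2-sided) to detect a treatment difference of 25" per cent.
- SD (Protocol 9.2): "the above variability was inflated by ~20%, and assumed to be 44% for the primary sleep parameter".
- Evaluable patients (Protocol 9.2): "a total sample of 150 (50 in placebo and 100 in dupilumab group"). SAP 3.1 gives the allocation: "randomly assigned to study intervention in a 2:1 dupilumab to placebo ratio".
- Dropout 20% and about 201 randomised (SAP 4.1).

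**Not in the documents:** dropout by arm or reason, the share of patients who stop but stay in follow-up, and rescue rates. Leaving rates on dupilumab are therefore assumptions and are shown as a range.

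**1. The plan's own power.** SE = 44 × √(1/50 + 1/100) = 7.62. Power = Φ(25/7.62 − 1.96) = Φ(1.32) = 0.907 (0.903 with the noncentral t). The stated 90% is reproduced.

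**2. Effect if dupilumab leavers follow the placebo course.** Let d be the share of dupilumab patients who leave. Those who remain keep a 25-point advantage and the leavers have none. Placebo leavers follow the placebo course either way. The effect is 25 × (1 − d). With no off-treatment data observed, the MAR model returns 25.

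| d | Basis | Effect | Gap from 25 |
|---|---|---|---|
| 5% | assumed | 23.75 | 1.25 |
| 10% | assumed | 22.5 | 2.5 |
| 20% | SAP 4.1 dropout, assumed to apply to dupilumab | 20.0 | 5.0 |
| 25.4% | (201 − 150)/201, loss implied by 150 evaluable | 18.65 | 6.35 |

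With a true effect of 20.0, power is Φ(20/7.62 − 1.96) = 0.75 at the precision of 150 patients. At the precision of 201 the SE is 44 × √(1/67 + 1/134) = 6.58 and power is 0.86.

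**3. Patients who stop but stay.** Their observed data enter the model and pull the leavers' implied course down. Suppose d = 20%, a further share r stops but is observed, and no one keeps any benefit off treatment. A simple calculation, ignoring individual histories, puts the MMRM effect at 25 × (1 − d − r)/(1 − d). The treatment-policy value is 25 × (1 − d − r).
- r = 5%: 25 × 0.75/0.80 = 23.4, against 18.75.
- r = 10%: 25 × 0.70/0.80 = 21.9, against 17.5.

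So the course given to leavers is mainly, not purely, on-treatment, and a gap of more than 4 points remains.

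**4. Shift needed to lose significance.** At an observed difference of 25 the lower 95% limit is 25 − 1.96 × 7.62 = 10.1. If only dupilumab leavers are made worse by δ, significance is lost at about δ = 10.06/d. That is 50 points at d = 20% and 40 points at d = 25.4%. The SE is held fixed, without added imputation variance.

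**5. What the planned analysis can detect.** Weeks after a patient leaves contribute no data to either fit, so dropping thin weeks cannot reveal the gap in step 2.

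**6. The rescue rules side by side.** Table 3.1.2 sets primary-endpoint data to missing after rescue. SAP 15.3.1, which applies to all efficacy endpoints, sets only AD assessments to missing after rescue. Its rule on sleep-affecting medication lists sleep assessments separately from AD assessments. Read literally, the two differ on whether the sleep quality NRS is kept after rescue.

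**The case against.** The strongest reply is that the plan is internally open. The strategy for an intercurrent event and the assumption for data that remain missing are separate choices, and Table 3.1.2 states both in one row. Collected off-treatment data are used, and the protocol works to keep patients in follow-up. A reader might infer that the primary analysis contradicts its declared estimand. The documents do not support that, because MAR for what stays missing is openly declared. What remains is that the assumption goes untested.

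A reader might also infer that leaving out post-rescue data is an error. It follows the declared hypothetical strategy for rescue. An MMRM on all data would answer a different question and would not test MAR. Nor can a loss of effect through rescue be put in figures from the documents, which give no rescue rates and no size of benefit from rescue.

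Thirdly, the 20% dropout figure has no arm, reason or treatment status attached. All of it occurring on dupilumab at that rate, for reasons other than Covid-19 and with full reversion to the placebo course, is unfavourable to the drug. This stands, and it is why step 2 is a conditional calculation and not a forecast.

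Finally, the result would be robust at the planned effect. Step 4 confirms it.

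**Conclusion.** The concern holds as a gap in robustness. The sole sensitivity analysis shares the MAR assumption with the primary, and nothing else in the plan departs from it. For leavers whose reason is not Covid-19, that assumption sits poorly with the treatment-policy aim.

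If dupilumab leavers took the placebo course, a planned 25 points would become 20.0 at 20% leavers, one fifth less, and 18.65 at 25.4%. Both figures rest on applying overall loss to the dupilumab arm and on complete reversion. Fewer leavers or partial reversion would give a smaller gap.

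It would be tempting to conclude that the significance of the trial is in doubt. At an observed effect of 25 it is not: dupilumab leavers would have to be about 40 to 50 points worse than MAR implies. Significance comes into question only if the observed effect is smaller. Whether post-rescue sleep scores are kept is unsettled until the two SAP passages are reconciled.

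**What to change.** Before database lock, which SAP section 1 sets as the limit for changes:

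- **SAP 8.1.5:** keep the thin-week analysis and add two analyses.
  - Reference-based multiple imputation (jump to reference) for patients who discontinue for reasons other than Covid-19 and have no Week 12 value.
  - A delta tipping-point analysis for dupilumab patients whose Week 12 value is missing, including values set to missing after rescue.
  - In both, Covid-19 stops stay under the declared hypothetical strategy with MAR. State which rule governs a patient who is rescued and then leaves.
- **SAP 8.1.6:** replace the not-applicable entry with a supplementary MMRM on all observed weekly averages, including those after rescue. Label it as a treatment-policy estimand for rescue, not as a test of MAR.
- **Table 3.1.2 and SAP 15.3.1:** reconcile the handling of the sleep quality NRS after rescue.
- **Reporting:** give the Week 12 difference and confidence interval from the jump-to-reference and all-data analyses beside the primary result, with the tipping shift.

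The cost is SAP text and some programming. No new data are needed, and the primary analysis, alpha and sample size are unchanged. The supportive estimates will probably be less favourable than the primary.

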8.1.6. Supplementary Analyses

Not applicable.

8.1.7. Impact of Covid-19 Pandemic

During the Covid-19 pandemic, a business continuity plan (BCP) was put in place to minimize the impact of the clinic visit interruption, ensure IMP treatment continuity and data collection. Direct to patient delivery of IMP from the site(s) was made available, home injection(s) were done as planned per protocol. IMP interruption due to Covid-19 pandemic is therefore expected to be minimum. Data collection for PROs are not expected to be missing as they can be completed at patient's home on his/her iPad. Site(s) can update/correct the schedule of completion if visit is rescheduled/delayed – unless site staff cannot access vendor platform to update scheduled dates.

Missing data due to Covid-19 pandemic is likely to be missing at random. Therefore, the primary analysis using MMRM can adequately address this type of missing data. Patient disposition by visit according to trial impact (disruption) due to COVID-19 and by country and site are already mentioned in [section 5.1](#) of this SAP.

8.2. Secondary and Exploratory Efficacy Endpoint

The secondary efficacy endpoints associated with “Change from baseline” and “Percent change from baseline” during the double-blind treatment period will be analyzed using the same approach as used for the analysis of the primary endpoint.

Definitions of endpoints are included in [Sections 15.8, 15.9 and 15.10](#).

8.2.1. Actigraphy data

SE, TST, WASO and SOL, all based on actigraphy data, will be summarized at each post-baseline visit (Week 1, Week 2, Week 3, Week 4, Week 8, Week 12, Week 16, Week 20, and Week 24).

In addition, at each post-baseline visit until Week 12, the change from baseline will be modelled using the same MMRM model used for the analysis of the primary endpoint. LS mean differences between the dupilumab and placebo group, the corresponding 95% CI of the differences and two-sided p-values will be provided. All p-values except for Week 12 will be considered nominal.

Change from baseline to Week 24 and Change from Week 12 to Week 24 will be summarized on the OLE analysis set using descriptive statistics in each treatment group (those originally randomized to in the double-blind study treatment period). No comparative statistical analyses will be done.

8.2.2. Sleep diary

SE, TST, WASO, SOL, number of awakenings and how rested the participant felt when getting up, all based on sleep diary data, will be summarized at each post-baseline visit (Week 1, Week 2, Week 3, Week 4, Week 8, and Week 12).

In addition, at each post-baseline visit, the change from baseline will be modelled using the same MMRM model used for the analysis of the primary endpoint. LS mean differences between the dupilumab and placebo group, the corresponding 95% CI of the differences and two-sided p-values will be provided. All p-values except for Week 12 will be considered nominal.

8.2.3. Sleep Quality NRS

Rescaled sleep Quality NRS (see [section 8.1](#)) will be summarized at each post-baseline visit (Week 1, Week 2, Week 3, Week 4, Week 8, Week 16, Week 20, and Week 24)

In addition, at each post-baseline visit until Week 12, the percent change from baseline will be modelled using the same MMRM model used for the analysis of the primary endpoint. LS mean differences between the dupilumab and placebo group, the corresponding 95% CI of the differences and two-sided p-values will be provided. All p-values except for Week 12 will be considered nominal.

Percent change from baseline to Week 24 and percent change from Week 12 to Week 24 will be summarized on the OLE analysis set using descriptive statistics in each treatment group (those originally randomized to in the double-blind study treatment period). No comparative statistical analyses will be done.

8.2.4. Peak Pruritus NRS

Peak pruritus NRS will be summarized at each post-baseline visit (Week 1, Week 2, Week 3, Week 4, Week 8, Week 12, Week 16, Week 20, and Week 24). Daily results for each day of Week 1 will also be provided.

In addition, at each post-baseline visit until Week 12, the percent change from baseline will be modelled using the same MMRM model used for the analysis of the primary endpoint. LS mean differences between

the dupilumab and placebo group, the corresponding 95% CI of the differences and two-sided p-values will be provided. All p-values except for Week 12 will be considered nominal.

Percent change from baseline to Week 24 and percent change from Week 12 to Week 24 will be summarized on the OLE analysis set using descriptive statistics in each treatment group (those originally randomized to in the double-blind study treatment period). No comparative statistical analyses will be done.

Times to pruritus improvement are defined as:

1. Time to achieving ≥ 3 points improvement in NRS [Time frame: Baseline till Week 4]
2. Time to achieving ≥ 4 points improvement in NRS [Time frame: Baseline till Week 4]

The time variable will be the first day of achieving $\geq x$ points improvement, and if that was not achieved during the first 4 weeks (where daily assessments were done), it will be censored at 28 days. Although the time variable is counting the number of days, the baseline will still be the weekly average at Visit 1 since that is the inclusion criteria and better represents the patient pruritus at baseline. The baseline date will be the date of Visit 1. Patients who discontinued for any reason within the first 4 weeks will be censored at the time of discontinuation.

The median time to pruritus improvement and proportion of patients achieving $\geq x$ points improvement at Week 1, Week 2, Week 3, and at Week 4 along with the corresponding 95% CI will be calculated using Kaplan Meier method.

A summary with the number of patients achieving the pruritus improvement, the number of censored patients, the median time, rates at Week 1, Week 2, Week 3, and Week 4 along with the corresponding 95% CI will be provided. Kaplan-Meier curves will be provided too.

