5.1 INCLUSION CRITERIA

Participants are eligible to be included in the study only if all of the following criteria apply:

Age

I 01. Participant must be 18 years of age or older, at the time of signing the informed consent

Type of participant and disease characteristics

- I 02. Participants with chronic AD that has been documented for at least 2 years before the screening visit
- I 03. Inadequate response to topical medications or otherwise candidate for systemic AD treatment
- I 04. Eczema Area Severity Index (EASI) score ≥ 12 at screening and baseline visits
- I 05. Investigator's global assessment (IGA) score ≥ 3 (on the 0 to 4 IGA scale) at the screening and baseline visits
- I 06. $\geq 10\%$ body surface area (BSA) of AD involvement at the screening and baseline visits
- I 07. Baseline pruritus NRS score for maximum itch intensity ≥ 3 (based on weekly average of daily scores during the 7 days immediately preceding baseline, or based on average of daily scores completed for 5 days (from Day -7 to Day -3 prior to baseline) for patients participating in the PSG sub-study; at least 4 ratings over the prior week/over the 5 days are required to calculate the average)
- I 08. Baseline Sleep Quality NRS score ≤ 5 (based on weekly average of daily scores during the 7 days immediately preceding baseline, or based on average of daily scores completed for 5 days (from Day -7 to Day -3 prior to baseline) for patients participating in the PSG sub-study; at least 4 ratings over the prior week/over the 5 days are required to calculate the average)
- I 09. Have been applying skin emollients (moisturizers) twice daily (once daily on areas receiving background topical medications – see [I 10](#) below and [Section 6](#)) for at least 7 days prior to randomization
- I 10. Have been applying medium-potency TCS on all active AD lesions, once daily for at least 7 days before randomization, using the standardized regimen provided in the protocol.

Note: Low-potency TCS or topical calcineurin inhibitor (TCI) may be used on areas that cannot be safely treated with medium- potency TCS (eg, face, genital, flexural areas, or areas of skin atrophy)

I 11. Willing and able to comply with all clinic visits and study-related procedures

Weight

Not applicable.

Sex

Male or female

Informed Consent

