day. The ESS score (the sum of 8 item scores, 0-3) can range from 0 to 24. The higher the ESS score, the higher that person's average sleep propensity in daily life, or their daytime sleepiness.

ESS score will be directly provided by KONEKSA.

Sleep Quality NRS

The Sleep Quality NRS is a simple assessment tool that patients will use to report the quality of patient's last night sleep. Patients will be asked the following question:

“On a scale of 0 to 10, with 0 being “worst possible sleep” and 10 being the “best possible sleep”, select the number that best describe the quality of your sleep last night”

Patients will complete the rating scale daily including 7 days immediately preceding the baseline visit (or daily for 5 days (from Day -7 to Day -3 prior to baseline) for patients participating in the PSG sub-study), and daily for 4 weeks (through visit 4), then daily during the week before each planned visit.

Instructions: Please complete the following question upon awakening for the day.

Select the number that best describe the quality of your sleep last night.

0	1	2	3	4	5	6	7	8	9	10	
Worst possible sleep											Best possible sleep

Patient chooses a value from 0 to 10 in the only question of the scale and that value is the global score of the scale.

Sleep Quality NRS score will be directly provided by KONEKSA.

Peak Pruritus NRS

The Peak Pruritus NRS is a simple assessment tool that patients will use to report the intensity of their pruritus (itch) during a daily recall period. Patients will be asked the following question:

“On a scale of 0 to 10, with 0 being ‘no itch’ and 10 being the ‘worst itch imaginable’ , how would you rate your itch at the worst moment during the previous 24 hours?”

Patients will complete the rating scale daily for 7 days prior to baseline (or daily for 5 days (from Day -7 to Day -3 prior to baseline) for patients participating in the PSG sub-study), and daily for 4 weeks (through visit 4), and then daily during the week before each planned visit.

On a scale of 0 to 10, with 0 being “no itch” and 10 being “worst itch imaginable”, how would you rate your itch at the worst moment during the previous 24 hours?

0	1	2	3	4	5	6	7	8	9	10
No itch										Worst itch imaginable

Patient chooses a value from 0 to 10 in the only question of the scale and that value is the global score of the scale.

Peak Pruritus NRS score will be directly provided by KONEKSA.

Skin Pain NRS

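### The time to a ≥4-point pruritus improvement keeps patients with a baseline below 4, who cannot have the event, so its response rates are diluted as estimates for patients able to respond

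*SAP*

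**What the plan says.** Protocol 5.1, criterion I07, sets the entry threshold: "Baseline pruritus NRS score for maximum itch intensity ≥ 3 (based on weekly average of daily scores during the 7 days immediately preceding baseline". Patients in the polysomnography sub-study use a five-day average with the same threshold.

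SAP 8.2.4 defines two times to pruritus improvement up to Week 4, one for ≥3 points and one for ≥4 points ("Time to achieving ≥ 4 points improvement in NRS"). The event is the first day on which the improvement is seen. The daily score is compared with an averaged baseline: "the baseline will still be the weekly average at Visit 1 since that is the inclusion criteria". SAP 15.8 gives the scale: "Patient chooses a value from 0 to 10 in the only question of the scale", with 0 meaning no itch.

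For a patient without the event in the first four weeks, the SAP says "it will be censored at 28 days". It adds: "Patients who discontinued for any reason within the first 4 weeks will be censored at the time of discontinuation". The planned output is descriptive. "The median time to pruritus improvement and proportion of patients achieving" the threshold at Weeks 1, 2, 3 and 4 are to be estimated by Kaplan-Meier with 95% confidence intervals, together with event and censoring counts and curves.

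SAP section 8 runs efficacy analyses on the mITT, OLE or PSG set. The mITT set (SAP 4.3.3) requires a baseline and one post-baseline measurement, with no minimum itch score. SAP 8.2.4 adds no baseline condition of its own.

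**The concern.** The entry threshold is 3 and the larger improvement threshold is 4, and both refer to the same averaged baseline. Patients with a baseline of 3 to below 4 are therefore eligible and are followed for an event that the scale does not allow them to have.

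At stake is how the output is read. The ≥3-point and ≥4-point results will appear as a pair describing how fast itch improves. By design every patient who meets I07 can reach the first threshold, but not every such patient can reach the second. Part of any gap between the two would then reflect where patients started and not how they responded. A reader who takes the ≥4-point rate as the chance of that response in someone able to show it would read a figure that is too low.

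**Working it through.** The SAP states no sample size, event rate or median for this variable, so there is no planned figure to reproduce. The check has four steps.

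**Inputs from the documents.** Minimum baseline 3 (I07); scale 0 to 10 (SAP 15.8); event threshold 4 points, averaged baseline and censoring at 28 days (SAP 8.2.4); 201 patients randomized 2:1 (SAP 3.1).

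**Inputs assumed.** f, the share with baseline below 4, is not in the documents; 0 to 20% is shown. The response rates of 40% and 60% are illustrations.

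**Step 1: who can have the event.** The largest possible improvement is baseline − 0 = baseline. Baselines of 3.0, 3.4 and 3.9 allow at most 3.0, 3.4 and 3.9 points, so none reaches 4. A baseline of 4.0 reaches it only with a daily score of 0. Any baseline of 3 or more can reach the ≥3-point threshold.

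**Step 2: effect on the rates.** If F(t) is the cumulative response among patients able to respond, the all-patient response is (1−f) × F(t). For a 40% rate:

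- f = 5%: 0.95 × 40% = 38%
- f = 10%: 0.90 × 40% = 36%

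**Step 3: effect on the median.** The all-patient median solves (1−f) × F(t) = 0.5. If F(28) is 40%, the median is not reached with or without the restriction. With F(28) = 60% and an assumed exponential time to event, the rate is −ln(0.4)/28 = 0.0327 per day, and the median is −ln(1 − 0.5/(1−f))/0.0327:

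| f | Day 28 rate, all patients | Median, all patients |
|---|---|---|
| 0% | 60.0% | 21.2 days |
| 5% | 57.0% | 22.8 days |
| 10% | 54.0% | 24.8 days |
| 15% | 51.0% | 27.1 days |
| 20% | 48.0% | not reached |

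**Step 4: does Kaplan-Meier itself go wrong?** In a simulation (134 patients, 5% random discontinuation, 60% true rate among patients able to respond, 400 runs), Kaplan-Meier in all patients gave 57.2%, 54.2% and 48.4% at f = 5%, 10% and 20%. The values of (1−f) × 60% are 57%, 54% and 48%. Restricted to patients able to respond, it gave 60.3%, 60.2% and 60.2%. The estimator therefore recovers the all-patient proportion; what changes is the population to which the number refers.

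**The case against.** The strongest reply is that nothing is misestimated. The SAP asks for a proportion of patients. Patients who start below 4 are true non-responders to a ≥4-point criterion and stay in the risk set until Day 28 or discontinuation. Keeping them preserves the mITT population used for the other efficacy analyses. This stands: a reader might call the curves biased, but Step 4 shows that they are consistent for the all-patient proportion. They are low only for a different target, patients able to respond, and the SAP does not say which of the two it means.

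Three further inferences are tempting and are not supported.

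- That the median is too long in both arms. This needs more than 50% of the patients able to respond in an arm to do so by Day 28, and the documents do not say that either arm will.
- That a planned treatment difference is shrunk. SAP 8.2.4 names no between-arm difference, log-rank test or hazard ratio for this variable. If someone subtracts the reported rates, with equal f in the arms, an assumed 45% versus 20% becomes 40.5% versus 18% at f = 10%. The difference falls from 25 to 22.5 points, but the ratio stays at 2.25.
- That I07 guarantees a baseline of at least 3 in the analysis. SAP 5.2 anticipates that an ineligible patient may be randomized. SAP 4.4.6 also averages the baseline by a different rule (at least 5 days) from I07 (at least 4 ratings).

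The size is also modest. With 201 × 2/3 = 134 dupilumab patients, a 40% rate has a 95% interval of about ±1.96 × √(0.4 × 0.6/134) = ±8 points, against a shift of 2 to 4 points at f = 5 to 10%.

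**Conclusion.** The point holds as a minor one. The ≥4-point analysis includes patients who cannot have the event, and nothing in the eligibility criteria, the mITT definition or SAP 8.2.4 removes them. As an estimate for patients able to respond, each Week 1 to 4 rate is diluted by (1−f). On the assumed 5 to 10%, that is 2 to 4 points on a 40% rate; if nobody enters below 4, it is nothing. The median moves, or ceases to be reached, only under the condition in Step 3.

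The variable is absent from the objectives table (SAP Table 3.1.1) and from the testing hierarchy (SAP 8.2.23), where the pruritus endpoint is percent change at Week 12. The primary result, the key secondary tests and the type I error are unaffected. Baseline precedes randomization, so f should be similar in the two arms.

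**What to change.** In SAP 8.2.4, restrict the ≥4-point analysis to patients whose baseline weekly average, as used for the event definition, is at least 4. Alternatively, keep the all-patient analysis and add the restricted one beside it. In either case report the number with baseline below 4 in each arm, so that f is visible. The ≥3-point analysis can keep all patients who meet I07.

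The cost is one sentence in the SAP and one filter on data already collected. The downside is a slightly smaller denominator and an analysis population that differs from mITT; presenting both versions deals with the second.
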